### **Rationale for Dose Range**

#### *Safety:*

A dose of 15 mg twice daily in humans is projected to produce a steady state  $AUC_{0-12}$  of 72  $\mu\text{g}\cdot\text{hr}/\text{mL}$ , based on modeling from Phase 1 PK data. The safety margin associated with this exposure is approximately 3-fold below the NOAEL exposure in rats, and 5-8-fold below the NOAEL exposure established in dogs.

#### *Efficacy:*

This study is designed to test CCX140-B at doses ranging from 5 mg twice daily through 15 mg twice daily, a dose projected to provide continuous high level receptor engagement and

antagonism.

The targeted dose was projected from observations in a murine model with features of FSGS, the adriamycin-induced nephropathy mouse model (Lee, et al., 2011). CCX140-B does not bind murine CCR2 and human CCR2 with the same potency, therefore the model was established in a CCR2 knockout and human CCR2 knock-in (hCCR2-KI) mouse. Mice were treated with 10, 30, and 90 mg/kg of CCX140-B once daily for 9 days. The 24 hour post last dose blood samples from 90 mg/kg dosing resulted in close to 100% receptor coverage. The mean CCX140-B concentration at trough was 3.3  $\mu$ g/mL (6.6  $\mu$ M).

In the absence of proteinuria, the human trough concentration with 15 mg twice daily dosing is projected to be ~5.5  $\mu$ g/mL, which is higher than the 3.3  $\mu$ g/mL required for 100% CCR2 blockade in the above described hCCR2 mouse model. However, the projected exposures and safety margins were established for humans without proteinuria. Because CCX140-B is highly protein bound, subjects with nephrotic-level proteinuria may have a lower exposure at a given dose due to potential drug loss with protein in urine or impact of disease on metabolism. A post-hoc analysis of PK in diabetic nephropathy subjects of trial CL005\_140 who entered in study with albuminuria of 2 – 3 grams indicated that exposure was approximately 30% below the mean for the treatment group as a whole (~0.8  $\mu$ g/mL versus ~1.2  $\mu$ g/mL).

Therefore 15 mg twice daily was selected as the upper limit for dose ranging for subjects with nephrotic level proteinuria.

## Dose Modification Rules

### **Dose Modification Rules for individual subjects**

Discontinue treatment with CCX140-B when a subject experiences any of the following events confirmed by repeat measurement after 2 weeks:

- Progression of renal disease, defined as eGFR that is both below 60 ml/min/1.73  $m^2$  and is confirmed to represent at least 30% decline in eGFR from baseline
- Requirement for rescue with glucocorticoids, other new immunomodulatory or immunosuppressive therapy, plasmapheresis or dialysis
- Pre-specified adverse event or laboratory abnormality that, per Protocol, requires permanent discontinuation of study CCX140-B
- Any other treatment-related adverse event, laboratory evidence of toxicity or intolerance that in the judgment of the investigator, warrants permanent discontinuation of CCX140-B

Halt treatment then alert sponsor and reassess after 1 week when there is a Clinical diagnosis of hemolysis in the judgment of the investigator, based on elevation of LDH, elevation of reticulocyte count, elevation of bilirubin and or other laboratory indications.

Consider discontinuation of treatment when a subject experiences any of the following events:

An increase of serum ALT to >3xULN should be followed by repeat testing within 48 to 72 hours of all four of the usual serum measures (ALT, AST, ALP, and TBL) to confirm the abnormalities and to determine if they are increasing or decreasing.

Discontinuation of treatment should be considered if:

- ALT or AST  $>8\times$ ULN
- ALT or AST  $>5\times$ ULN for more than 2 weeks
- ALT or AST  $>3\times$ ULN and (TBL  $>2\times$ ULN or INR  $>1.5$ )
- ALT or AST  $>3\times$ ULN with the appearance of fatigue, nausea, vomiting, right upper quadrant pain or tenderness, fever, rash, and/or eosinophilia ( $>5\%$ )

Halt treatment then alert sponsor and reassess after 2 weeks whenever a subject has either

- Hemoglobin reduced from baseline by  $\geq 2$  g/L and deemed clinically significant by the PI
- An increase in reticulocyte count by  $\geq 2\%$  (absolute) from baseline that is not otherwise explained
- $\geq$  moderate symptoms limiting instrumental activities of daily living or asymptomatic (based on diagnostic evaluation only) and deemed clinically significant by the investigator
- Any adverse events assessed as moderate, related to study drug, and clinically significant

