## Dose and Dose Adjustments

Eligible subjects will start treatment with CCX140-B at 5 mg twice daily. CCX140-B will be taken orally without food, at least one hour before a meal. The dose may be increased in a stepwise manner to 10 mg twice daily on day 15, then to 15 mg twice daily on day 43 while monitoring efficacy, PK and safety. Dose escalations will occur in accordance with the rules and schedule detailed in [Table 1](#), [Figure 1](#) and [Section 7.5.1](#). Dose may be adjusted downward in the event of intolerance, laboratory evidence of toxicity, or a measured or projected steady state exposure that exceeds the pre-specified maximum safe exposure based on the No Observed Adverse Event Level (NOAEL) established in the non-clinical toxicology program.

In all subjects, treatment at the selected dose will be continued through 12 weeks or until declaration of Treatment Failure, where Treatment Failure is defined as any of the following:

- 1) Progression of renal disease, defined as eGFR that is both below 60 ml/min/1.73 m^2 and is confirmed to represent at least a 30% decline in eGFR from baseline;
- 2) Requirement for rescue with glucocorticoids, other new immunomodulatory or immunosuppressive therapy, plasmapheresis, or dialysis, per the judgment of the Investigator;
- 3) Pre-specified adverse event or laboratory abnormality that, per Protocol, requires permanent discontinuation of study CCX140-B
- 4) Any other treatment-related adverse event, laboratory evidence of toxicity, or intolerance that, in the judgment of the Investigator, warrants permanent discontinuation of CCX140-B.

If planned dose escalation to 10 mg (on day 15) or 15 mg twice daily (on day 43) was previously halted the dose may be escalated further if subjects are not considered treatment failures and who otherwise meet criteria for continuation. In such case the subject will return approximately 2 weeks later for blood draws to assess PK (AUC0-6). Subjects will return 2 weeks after the PK assessment to evaluate the safety and need for further dose adjustment.

Subjects who completed 12 weeks of treatment are not considered treatment failures and who otherwise meet criteria for continuation may be extended for up to an additional 40 weeks to assess degree and duration of response. During the extension period the dose may be adjusted if indicated based on assessment of safety, PK and efficacy. (see [Table 1](#) and [Figure 1](#) for

guidelines).

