**Figure 1: Study Schematic****Treatment failure = Tx failure:**

1. Progression of renal disease, defined as eGFR that is both below 60 ml/min/1.73 m^2 and is confirmed to represent at least a 30% decline in eGFR from baseline;
2. Requirement for rescue with glucocorticoids, other new immunomodulatory or immunosuppressive therapy, plasmapheresis, or dialysis, per the judgment of the Investigator;
3. Pre-specified adverse event or laboratory abnormality that, per Protocol, requires permanent discontinuation of study CCX140-B
4. Any other treatment-related adverse event, laboratory evidence of toxicity, or intolerance that, in the judgment of the Investigator, warrants permanent discontinuation of CCX140-B.

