### **3. STUDY DESIGN AND DOSING REGIMEN**

#### **3.1. Initial Treatment Phase**

This is an open label clinical trial to test the efficacy, safety, pharmacokinetics and tolerability of ascending doses of CCX140-B in subjects with primary FSGS and nephrotic syndrome.

The screening period will be up to 28 days. Subjects will visit the study center during Screening and on Day 1 (baseline), weekly throughout Dose Escalation, then every 2 weeks through Study Week 12.

Eligible subjects will start treatment with CCX140-B at 5 mg twice daily. CCX140-B will be taken orally without food, at least one hour before meal. The dose will be increased in a stepwise manner to 15 mg twice daily while monitoring safety, in accordance with the rules ([Table 1](#) and [Figure 1](#)) and schedule detailed in the [Time and Events Table](#). Treatment at the selected dose will be continued up to Week 12 or until declaration of Treatment Failure.

This study incorporates intra-subject dose escalation and dose modification. Four factors guide dose modification including:

1. Time
2. Response
3. Exposure
4. Safety

During the initial 12 weeks of treatment, dose will be escalated from 5 mg twice daily to 10 mg twice daily on Study Day 15, then to 15 mg twice daily on Study Day 43, if subjects are not considered treatment failures and who otherwise meet criteria for continuation ([Table 1](#), [Figure 1](#)).

If planned dose escalation to 10 mg (on day 15) or 15 mg twice daily (on day 43) was previously halted the dose may be escalated further if subjects are not considered treatment failures and who otherwise meet criteria for continuation ([Table 1](#), [Figure 1](#)). In such case the subject will return approximately 2 weeks later for blood draws to assess PK (AUC0-6). Subjects will return 2 weeks after the PK assessment to evaluate the safety and need for further dose adjustment.

At any time during the study dose may be de-escalated for safety, or if projected exposure exceeds the maximum allowable exposure defined for the study. Because exposure may be impacted by changes in proteinuria, the protocol requires assessment of exposure if proteinuria declines significantly.

Blood will be drawn to evaluate trough exposure in accordance with the Time and Events Schedule. In addition, as detailed in [Table 1](#), blood will be drawn to assess exposure (AUC0-12, extrapolated from measured AUC0-6), at the following times to guide dosing decisions:

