In all subjects, treatment at the selected dose will be continued through 12 weeks or until declaration of Treatment Failure, where Treatment Failure is defined as any of the following:

1. Progression of renal disease, defined as eGFR that is both below 60 ml/min/1.73 m^2 and is confirmed to represent at least a 30% decline in eGFR from baseline;
2. Requirement for rescue with glucocorticoids, other new immunomodulatory or immunosuppressive therapy, plasmapheresis, or dialysis, per the judgment of the Investigator;
3. Pre-specified adverse event or laboratory abnormality that, per Protocol, requires permanent discontinuation of study CCX140-B
4. Any other treatment-related adverse event, laboratory evidence of toxicity, or intolerance that, in the judgment of the Investigator, warrants permanent discontinuation of CCX140-B.

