### 7.7.1. Rescue Therapy

If the investigator decides that a subject needs to receive rescue therapy the subject will be considered a treatment failure. Rescue therapy is considered any new therapy or required dose increase of an existing concomitant therapy (other than allowed per [Section 7.7. Concomitant](#)

Medications and Restrictions) that is required for the safety of the patient and to treat the underlying disease of FSGS.

This would include but is not limited to the initiation of high dose glucocorticoid therapy, new immunosuppressive agents such as calcineurin inhibitors, cyclophosphamide, MMF, monoclonal antibodies, or other major treatments (e.g. plasmapheresis, dialysis).

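### The synopsis stopping rule asks for a two-week repeat measurement before discontinuing for need of rescue or clinical toxicity, where the Treatment Failure definition asks for no confirmation

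*Protocol*

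**What the plan says.** The protocol synopsis, under the dose modification rules for individual subjects, begins: "Discontinue treatment with CCX140-B when a subject experiences any of the following events confirmed by repeat measurement after 2 weeks". Four bullets follow:

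1. progression of renal disease by eGFR;
2. "Requirement for rescue with glucocorticoids, other new immunomodulatory or immunosuppressive therapy, plasmapheresis or dialysis";
3. a pre-specified adverse event or laboratory abnormality for which the protocol requires permanent discontinuation;
4. "Any other treatment-related adverse event, laboratory evidence of toxicity or intolerance that in the judgment of the investigator, warrants permanent discontinuation of CCX140-B".

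The same four events define Treatment Failure in the protocol (synopsis on dose and dose adjustments, Figure 1 legend, Section 5.2.1) and in the SAP (Figure 1 legend, Section 2.2.3). There, only the eGFR item carries confirmation, in the words "is confirmed to represent at least a 30% decline in eGFR from baseline", and no interval is given. The rescue item reads "Requirement for rescue with glucocorticoids, other new immunomodulatory or immunosuppressive therapy, plasmapheresis, or dialysis, per the judgment of the Investigator".

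Treatment Failure also acts as a stopping rule. The synopsis says that "treatment at the selected dose will be continued through 12 weeks or until declaration of Treatment Failure", and Section 3.1 says "Treatment at the selected dose will be continued up to Week 12 or until declaration of Treatment Failure". Section 7.7.1 adds: "If the investigator decides that a subject needs to receive rescue therapy the subject will be considered a treatment failure".

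**The concern.** One protocol gives two different conditions for permanently stopping drug on the same events. The synopsis wants a repeat measurement two weeks later for each of them. The Treatment Failure text wants confirmation of the eGFR decline only.

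The repeat does not suit the rest of the list. A need for dialysis or glucocorticoids is a clinical decision, with no value to measure again. An intolerance that the investigator already judges serious enough for permanent discontinuation gains nothing from a fixed two-week check. Two sites could stop drug at different times for the same event, each able to point to the protocol. What is at stake is the clarity of an individual-subject safety rule.

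**Working it through.** The plan states no figure to reproduce. The check is a comparison of texts, with two small counts.

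**Step 1. The four events side by side.**

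| Event | Synopsis discontinuation rule | Treatment Failure definition | Result |
|---|---|---|---|
| 1. eGFR progression | Repeat after 2 weeks | Confirmed, interval not stated | Both confirm; only the interval differs |
| 2. Need for rescue or dialysis | Repeat after 2 weeks | Investigator judgment, no confirmation | Conflict |
| 3. Pre-specified adverse event or laboratory abnormality | Repeat after 2 weeks | None stated; timing can come from the rule that pre-specifies the event | Conflict for purely clinical events only |
| 4. Other treatment-related event, toxicity or intolerance | Repeat after 2 weeks | Investigator judgment, no confirmation | Conflict for purely clinical events and intolerance |

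On explicit wording, confirmation is required for 4 of 4 events in the synopsis rule and 1 of 4 in the definition, so the wording differs for 4 − 1 = 3 events. In substance the conflict is complete for one event (2) and partial for two (3 and 4).

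**Step 2. When does drug stop under the Treatment Failure text?** For rescue, Section 7.7.1 makes the decision itself a treatment failure. The synopsis, Section 3.1 and Section 5.2.1 end treatment at declaration of failure. No repeat stands between the two. These sentences are written for the initial 12-week period, so the inference is limited to that period.

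**Step 3. Does Table 2 (Section 7.5) supply a general two-week repeat that the lead-in could be summarising?** Its 11 rows divide as follows:

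- repeat after 2 weeks: 2 rows (serum creatinine, UPCR);
- confirmation within 2 weeks, which is a deadline and not a waiting period: 1 row (ALT or AST at least 5 times ULN);
- confirmation within 72 hours: 3 rows (ALT or AST at least 8 times ULN; at least 3 times with bilirubin or INR; at least 3 times with symptoms or eosinophilia);
- halt drug first, then reassess after 1 or 2 weeks: 5 rows (hemolysis, anemia, reticulocytes, neuropathy, other clinically significant events).

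Check: 2 + 1 + 3 + 5 = 11. Both rows with the waiting-period repeat are laboratory values, and no row covers rescue. Table 2 therefore supports retests for some laboratory criteria and no general two-week confirmation.

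**Step 4. Size of the possible delay.** Upper bound, synopsis read literally: 2 weeks × 7 = 14 days. Lower bound, sites follow the Treatment Failure text: 0 days. The study has at most 6 + 7 = 13 subjects.

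**The case against.** The strongest reply is that no sensible site would apply the clause literally. A need for dialysis cannot be re-measured, the clause appears as a general lead-in only in the synopsis, and every restatement of Treatment Failure agrees with the others. The halt rules and the Safety Review Committee's review of serious adverse events as they occur give further cover. All of this stands and keeps the matter small. It does not remove the contradiction, because the narrower reading is not written and the documents do not say which text prevails.

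A second reply is that the third event takes its timing from other protocol rules, some of which carry their own retest, and that laboratory toxicity within the fourth may reasonably be rechecked. This also stands, and it is why the point is confined to rescue and purely clinical events.

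A reader might go further in three ways that the documents do not support:

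- **That the protocol keeps subjects on drug for two weeks, or delays their rescue.** The lead-in says when to discontinue. It neither orders dosing to continue nor forbids stopping earlier, and it says nothing about withholding rescue treatment.
- **That efficacy results are affected.** Failure status enters the efficacy definitions through partial and complete remission. SAP Section 3.4 says that neither of these, nor time to rescue, will be calculated.
- **That severe events are left without a stopping rule.** The general halt rule does name moderate related events only, while Section 7.3.1 grades severe and life-threatening events separately. That is a question about a different rule and adds no support here.

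**Conclusion.** The inconsistency is real and limited. As written, the synopsis lead-in contradicts the Treatment Failure text for need of rescue or dialysis, and for purely clinical adverse events or intolerance within the third and fourth events. It would overstate the point to say that three of the four events conflict outright.

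The possible delay in permanent discontinuation is 0 to 14 days. The 14 days assume a literal reading; the 0 days assume that sites follow the Treatment Failure text during the initial 12 weeks. SAP Section 1 reports that enrollment was not continued, which narrows the practical reach. It does not make the rule consistent, and that section does not say that dosing of enrolled subjects had stopped. Confidence in the wording mismatch is high; the safety consequence is small. This is a minor safety-rule correction.

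**What to change.** - **Move the clause.** Remove the two-week repeat from the synopsis lead-in and attach it to the eGFR bullet. Use the same interval wherever the Treatment Failure definition appears: protocol synopsis, Figure 1 and Section 5.2.1; SAP Figure 1 and Section 2.2.3.
- **Keep the laboratory retests.** Leave the intervals in Table 2 and the 48 to 72 hour liver retest as they are.
- **Add a statement along these lines.** A subject who needs rescue, or who has a clinical event or intolerance warranting permanent discontinuation, stops CCX140-B when failure is declared, with no two-week repeat. Subjects who add an immunosuppressive or immunomodulatory agent without meeting Treatment Failure remain under the existing Section 7.7 provision.

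The cost is a short text change, with no effect on visits, data collection, sample size or analysis. Because it alters a discontinuation rule, it may count as an amendment bearing on subject risk, which under Section 10.4 needs IRB/EC approval before it takes effect.

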### **Dose Modification / Stopping Rules for the overall study**

A dose will be considered as potentially exceeding the maximum tolerated dose should any of the following events occur:

- 2 or more subjects with confirmed QTcF prolongation  $\geq 450$  msec and an increase from baseline of  $\geq 30$  msec, based on triplicate 12-lead ECGs that is not otherwise explained
- 2 or more subjects with clinically significant hemolytic anemia, defined as hemoglobin that has declined from baseline by at least 2 grams/deciliter and is less than or equal to 8 g/dL and is assessed by the investigator and is not otherwise explained
- 2 or more subjects with bilirubin greater than 3 times upper limit of normal, and not ascribable to Gilbert's disease
- 2 or more subjects with new motor neuropathy or sensory neuropathy that limits instrumental activities of daily living and is assessed by the Investigator as clinically significant
- 2 or more subjects who require dose reduction or discontinuation due to adverse events assessed as possibly related to Study Drug, where the adverse events are medically similar events in the same System Organ Class based on MedDRA criteria

If a dose is assessed to be above the maximum tolerated dose, dosing will be reduced to the next lower dose.

A Safety Review Committee (SRC) comprising the Sponsor Study Director, Medical Monitor, at least one external expert nephrologist, and the Study Statistician will review all safety events described in the dose modification rules and all serious adverse events as they occur. The SRC will periodically review all adverse events and all laboratory abnormalities. The SRC may declare a dose to be above the maximally tolerated dose based either on the defined rules or on other considerations.

**Number of Subjects**

Six (6) male or female adult subjects with biopsy-proven primary FSGS and nephrotic syndrome will be enrolled in the first stage of this study. An additional 7 subjects may be enrolled in the second stage of this study based on observations in the first 6 subjects, as described in the sample size section of this protocol.

**Main Criteria for Inclusion**

1. Male or female subjects aged 18 years and older
2. Renal biopsy findings consistent with diagnosis of primary focal segmental glomerulosclerosis (FSGS) and consistent with primary FSGS based on presentation of histopathology, medical history and clinical course; subjects with genetic risk factors with presentations that are otherwise consistent with primary FSGS may also be enrolled.
3. Urinary total protein:creatinine ratio (UPCR)  $\geq 3.5$  g protein/g creatinine at screening, based on sample drawn from a 24-hour collection
4. Hypoalbuminemia of less than 3.5 g/dL
5. Estimated glomerular filtration rate (eGFR)  $> 30$  mL/min/1.73m^2, as calculated using the Chronic Kidney Disease Epidemiology Collaboration (CKD-EPI) equation (using creatinine or cystatin C)
6. If used, RAAS inhibitor dose, including doses of angiotensin converting enzyme inhibitor and/or angiotensin II receptor antagonist, must have been started at least 4 weeks prior to Study Day 1, and projected to remain stable throughout the course of the study unless adjustment is required for management of hypertension
7. Female subjects of childbearing potential may participate if adequate contraception is used during, and for at least 5 half-lives after last dose of study drug. Male subjects with partners of childbearing potential may participate in the study if they had a vasectomy at least 6 months prior to randomization or if adequate contraception is used during, and for at least one month after the last dose of study drug. Adequate contraception is defined as resulting in a failure rate of less than 1% per year (combined estrogen and progestogen [oral, intravaginal, or transdermal], or progestogen-only hormonal contraception (oral, injectable, or implantable), intra-uterine device, intra-uterine hormone releasing system, bilateral tubal occlusion, vasectomized partner, or sexual abstinence). In addition, a barrier method (i.e. cervical cap, diaphragm or condom) must be used during intercourse between a male subject and a female of child-bearing potential.
8. Willing and able to give written Informed Consent and to comply with the requirements of the study protocol.
9. Judged to be otherwise fit for the study by the Investigator, based on medical history, physical examination, and clinical laboratory assessments. Subjects with clinical laboratory values that are outside of normal limits (other than those specified in the Exclusion Criteria) and/or with other abnormal clinical findings that are judged by the Investigator not to be of clinical significance, may be entered into the study.

